### **3.2 Intervention**

Ruxolitinib will be administered as 5 mg (or if necessary, 25 mg) tablets taken orally at doses indicated in table 1 on page 14, approximately every 12 hours for 28 days every cycle. Decitabine is administered intravenously at a dose of 20mg/m^2 daily for 5 days per cycle. Subsequent cycles may be administered at 4-6 week intervals as clinically tolerated with a provision to start early if in the best interest of the patient after discussion with the principal investigator.

## **4.0 THERAPEUTIC AGENTS**

## 4.1 Ruxolitinib

Ruxolitinib represents a novel, potent, and selective inhibitor of JAK1 ( $IC_{50} = 3.3 \pm 1.2$  nM) and JAK2 ( $IC_{50} = 2.8 \pm 1.2$  nM) with modest to marked selectivity against TYK2 ( $IC_{50} = 19 \pm 3.2$  nM) and JAK3 ( $IC_{50} = 428 \pm 243$  nM), respectively. INCB018424 is inactive (ie, < 30% inhibition) against 28 additional kinases when tested at 200 nM.

Ruxolitinib has high solubility and permeability, (ie, it is designated as a Class I molecule in the Biopharmaceutical Classification System (BCS)) and exhibits moderate- to-high clearance, volume of distribution and oral bioavailability in preclinical species. The apparent elimination half-life is short (< 5 hr) in all species. The primary clearance pathway is oxidative metabolism. The metabolism by human liver microsomes is catalyzed predominantly by CYP3A4. In a study using C-Ruxolitinib in healthy volunteers, unchanged Ruxolitinib was the predominant circulating drug-related entity with 2 major circulating metabolites observed, both of which are mono-oxidation products. The metabolites of Ruxolitinib retain varying degrees of JAK-related pharmacological activity. Excretion was fairly rapid by both urinary and fecal routes with parent drug accounting for < 1% of the administered dose. Tissue distribution studies in rats indicate rapid and complete elimination of radioactivity in most tissues. Ruxolitinib exhibits high plasma protein binding in humans with an unbound fraction of 3.3%.

### 4.1.1 Chemistry

The chemical name of ruxolitinib, previously known as INCB018424 (also referred to as INC424) phosphate is (*R*)-3-(4- (7*H*-pyrrolo[2,3-*d*]pyrimidin-4-yl)-1*H*-pyrazol-1-yl)-3-cyclopentylpropanenitrile phosphate. INCB018424 phosphate has a molecular formula of C17H21N6O4P and a molecular weight of 404.36.

### 4.1.2 Physical Properties

Ruxolitinib is a white to off-white powder.

### 4.1.3 Stability

Based on available stability data, the drug product should be stored in high density polyethylene (HDPE) bottles with induction sealing and child-resistant closure between 15°C and 30°C.

### 4.1.4 Formulation

Ruxolitinib is provided as 5 mg, 10 mg, 15 mg, 20 mg and 25 mg strength tablets. The tablet formulations contain the active ingredient and may include the following commonly used excipients: microcrystalline cellulose, lactose, stearic acid, magnesium stearate, colloidal silicone dioxide, sodium starch glycolate, Povidone and hydroxyl propyl cellulose. All excipients are of US and EuPh compendial grade.

#### **4.1.5 FDA approval status and IND issues**

Ruxolitinib was approved by the FDA with the trade name, Jakafi, for the treatment of patients with intermediate or high-risk myelofibrosis.

#### **4.1.6 Decitabine**

Decitabine is a cytidine antimetabolite analogue that is believed to exert its antineoplastic effects after phosphorylation and direct incorporation into DNA and inhibition of DNA methyltransferase, causing hypomethylation of DNA and cellular differentiation or apoptosis. Decitabine inhibits DNA methylation *in vitro*, which is achieved at concentrations that do not cause major suppression of DNA synthesis. Decitabine-induced hypomethylation in neoplastic cells may restore normal function to genes that are critical for the control of cellular differentiation and proliferation. In rapidly dividing cells, the cytotoxicity of decitabine may also be attributed to the formation of covalent adducts between DNA methyltransferase and decitabine incorporated into DNA. Non-proliferating cells are relatively insensitive to decitabine. Decitabine is approved by the FDA for the treatment of patients with myelodysplastic syndromes.

#### **4.1.7 Chemistry and Physical Properties**

Decitabine is also known as 5-aza-2'-deoxycytidine, an analogue of the natural nucleoside 2'-deoxycytidine. Decitabine is a fine, white to almost white powder with the molecular formula of C8H12N4O4 and a molecular weight of 228.21. Its chemical name is 4-amino-1-(2-deoxy- $\beta$ -D-erythro-pentofuranosyl)-1,3,5-triazin-2(1H)-one. Decitabine is slightly soluble in ethanol/water (50/50), methanol/water (50/50) and methanol; sparingly soluble in water and soluble in dimethylsulfoxide (DMSO).

#### **4.1.8 Formulation and Stability**

Decitabine for injection is supplied as Dacogen™, a sterile lyophilized white to almost white powder, in a single-dose vial, packaged in cartons of 1 vial. Dacogen™ (decitabine) for Injection is a sterile lyophilized powder supplied in a clear colorless glass vial. Each 20 mL, single dose, glass vial contains 50 mg decitabine, 68 mg monobasic potassium phosphate (potassium dihydrogen phosphate) and 11.6 mg sodium hydroxide (**NDC 58063- 600-50**). Vials are to be stored at 25°C (77°F) with excursions permitted to 15-30°C (59-86°F). Unless used within 15 minutes of reconstitution, the diluted solution must be prepared using cold (2°C - 8°C) infusion fluids and stored at 2°C - 8°C (36°F - 46°F) for up to a maximum of 7 hours until administration.

#### **4.1.9 FDA approval status**

Decitabine was approved as Dacogen™ by the FDA for treatment of patients with myelodysplastic syndromes (MDS) including previously treated and untreated, de novo and secondary MDS of all French-American-British subtypes (refractory anemia, refractory anemia with ringed sideroblasts,

refractory anemia with excess blasts, refractory anemia with excess blasts in transformation, and chronic myelomonocytic leukemia) and intermediate-1, intermediate-2, and high-risk International Prognostic Scoring System groups. The indication of refractory anemia with excess blasts in transformation has been included in the definition of acute myeloid leukemia according to the most recent WHO classification. As a result, decitabine is a common treatment of AML, and has been incorporated into standard treatment pathways for AML by the National Comprehensive Cancer Network, especially in patients who are unfit for standard therapies, such as those over age 60 years.

## **5.0 ELIGIBILITY CRITERIA**

### **5.1 Inclusion Criteria**

1. Diagnosis of AML (WHO classification definition of  $\geq 20\%$  blasts).
2. In the phase I portion of the study all patients with relapsed or refractory AML are eligible. For the Phase II portion of the study, patients must have AML progressing from prior MPN (MPN-BP) or have MDS/MPN with more than 20% blasts..  
Temporary prior measures to control blood counts, such as apheresis or hydrea are allowed. Patients with newly diagnosed or previously treated disease are eligible as long as prior therapy does not include hypomethylating agents.Prior therapy for RUXOLITINIB for MPN is allowed.
3. Serum biochemical values with the following limits unless considered due to leukemia:
  - creatinine  $\leq 1.5$  mg/dl
  - total bilirubin  $\leq 1.5$  mg/dL, unless increase is due to hemolysis or congenital disorder
  - transaminases (SG PT)  $\leq 2.5 \times$  ULN
4. Ability to take oral medication.
5. Ability to understand and provide signed informed consent.
6. Performance status  $\leq 3$ , unless directly related to disease process as determined by the Principal Investigator
7. Age  $\geq 18$  years

### **5.2 Exclusion Criteria**

1. Any coexisting medical condition that in the judgment of the treating physician

is likely to interfere with study procedures or results including uncontrolled severe infections, as well as uncontrolled cardiac disease, or other organ dysfunction. Patients with history of tuberculosis, HIV or hepatitis B and C are excluded.

2. Nursing women, women of childbearing potential with positive blood pregnancy test within 30 days of study start, or women of childbearing potential who are not willing to maintain adequate contraception (such as birth control pills, IUD, diaphragm, abstinence, or condoms by their partner) over the entire course of the study..

3. Incomplete recovery from any prior surgical procedures or had surgery within 4 weeks prior to study entry, excluding the placement of vascular access.

4. Active clinically serious and uncontrolled infection

## 6.0 RECRUITMENT PLAN

Patients will be recruited among the patients referred to the Leukemia Department at the University of Texas – MD Anderson Cancer Center. There will be no direct advertising for this study. The study will be available to the public and the details of the inclusion criteria, exclusion criteria and study design will be posted at [www.clinicaltrials.gov](http://www.clinicaltrials.gov). A maximum of 36 patients (up to 12 patients in phase I and up to 24 patients in the phase II) will be enrolled in the study. Up to 6 patients can be replaced in the phase I portion of the study.

## 7.0 PRETREATMENT EVALUATION

The following tests must be done within 30 days of entry:

- A complete history and physical exam including ECOG performance status assessment and manual measurement (in cm) of the liver and spleen from the costal margin, if palpable.
- CBC with differential, comprehensive metabolic panel, LDH, direct bilirubin, phosphorus, albumin, uric acid, coagulation profile (PT, aPTT, fibrinogen), and  $\beta$ HCG (for pre-menopausal females),
- HIV and Hepatitis B and C testing
- Chest X-ray (PA and lateral)
- Abdominal imaging (only if clinically indicated, e.g. organomegaly)
- Bone marrow aspirate
  - Cytogenetics, and if necessary, FISH analysis (if insufficient aspirate, these tests can be performed in peripheral blood samples)
  - $JAK2^{V617F}$  and  $MPL^{W515L/K}$  mutation analysis and allele burden (if insufficient aspirate, these tests can be performed in peripheral blood samples)
- Bone marrow biopsy (including reticulin stain to assess the degree of fibrosis)

- )
- Peripheral blood sample for scientific correlative studies: one red top tube (10ml) and two purple top tubes (10ml each)
- ECG, MUGA/Echo
- CT/MRI abd/pelvis without contrast, if clinically indicated
- Pregnancy test performed only on women of child-bearing potential.

## 8.0 TREATMENT/INTERVENTION PLAN

### 8.1 Treatment Schedule

#### Phase I

Assuming MTD is not achieved, the first 9 patients on study will receive RUXOLITINIB for 28 days during induction therapy at escalating doses per the table below, plus

Decitabine 20 mg/m^2 IV daily for 5 days

Dose of RUXOLITINIB will be as follows:

**Table 1 – RUXOLITINIB dose**

Dose level	RUXOLITINIB (mg PO) (x 28 days)	No of evaluable patients
0	10 BID	3
1	15 BID	3
2	25 BID	3
3	50 BID	3

We will utilize the above design format to determine the tolerable dose of RUXOLITINIB to be used in combination with decitabine, with 25 mg PO BID as the target dose. The enrollment of participants will be staggered; all the participants in each cohort will finish the first cycle of therapy followed by 7 days of observation (i.e. day 35 of therapy) before proceeding to the next cohort. Subsequence cycles will begin on the first day of decitabine therapy and, in the absence of toxicity, RUXOLITINIB administration will not be interrupted. Patients who come off the study during the first cycle for reasons other than development of dose limiting toxicity (e.g. disease progression) will be replaced in order to ensure adequate chance for the assessment of DLT.

If grade 3-4 non-hematological RUXOLITINIB-related toxicities are observed in ≥ 2/6 patients, this dose level would exceed the MTD.

If grade 3-4 RUXOLITINIB-related toxicities are observed in 0-1/6 patients, the study will continue at the RUXOLITINIB dose of 15, 25, and 50 mg P.O. BID x 28 days plus chemotherapy, as outlined above. We will examine the dose of 50 mg BID to assess its tolerability and if well tolerated, this will be the dose to move to phase II. However, the target dose for phase II is 25 mg po BID x 28 days.

Cycles will be repeated approximately every 4 to 6 weeks, depending on the recovery of the blood counts and will continue until clinically significant progression, withdrawal of consent or unacceptable toxicity for a maximum of 24 cycles (see section 13.0).

Toxicities to be monitored include any grade 3 or 4 non-hematological toxicity felt to be related to RUXOLITINIB and prolonged cytopenias (lasting for more than 42 days after the initiation of the treatment) felt to be related to the treatment and not the underlying disease. Patients with prolonged cytopenias should have a bone marrow exam around day 42 to establish whether this is due to the treatment or whether there is persistent disease. In the case of the former, treatment should be discontinued.

Prior to advancing/changing dose levels, a cohort summary must be completed and submitted to the IND Medical Monitor for review.

Each cohort will have up to 6 patients enrolled.

## **Phase II**

Twenty four patients (not including any patients from the phase I portion of the study) will receive cycles of therapy according to the following starting schedule:

RUXOLITINIB at dose defined by Phase I portion of the study, on days 1-28 of each cycle

Decitabine 20 mg/m^2 IV daily for 5 days

Cycles will be repeated every 4 to 6 weeks depending on tolerance and the recovery of counts.

RUXOLITINIB will be provided by the sponsor (Incyte) free of charge to the participating patients for a maximum period of up to 24 months. Any used or expired study drug will be disposed of accordance to the MD Anderson policy.

## **Dose modifications during induction therapy in phase I and II:**

Patients who experience RUXOLITINIB-specific (defined as determined by the principal investigator) grade 3-4 extramedullary toxicities during induction cycle #1, and who are not in CR after cycle #1, may receive a second induction course at the next lower dose with respect to RUXOLITINIB (as defined in table1 on page 14). Other dose modification schedules felt to be in the best interest of the patient may be permitted, after discussion with the principal investigator with the documentation of the discussion in the patient's medical records. There will be no dose modifications of decitabine for either induction cycle #1, or second induction course, secondary to myelosuppression.

Adjustment of dose of RUXOLITINIB to 15 mg BID or 10 mg BID are acceptable in patients who have toxicity but are having benefit from the treatment. If patients develop significant myelosuppression that is thought to be specifically related to RUXOLITINIB, it can be held for a week and then resumed at a lower dose (5-10 mg per day less than the prior dose).

Toxicities to be monitored include any grade 3 or 4 non-hematological toxicity felt to be related to RUXOLITINIB and prolonged cytopenias (lasting for more than 42 days after the initiation of the treatment) felt to be related to the treatment and not the underlying disease. Patients with prolonged cytopenias should have a bone marrow exam around day 42 to establish whether this is due to the treatment or whether there is persistent disease. In the case of the former, treatment should be discontinued.

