#### **Phase I study**

Nine to 12 patients will be treated. Open study to phase II if first cycle RUXOLITINIB attributable toxicity in  $\leq 2$  of 6. If first cycle RUXOLITINIB-related DLTs are observed in more than 2/6 patients, this dose level would exceed the MTD, and 3 patients will be treated at the next lower dose level according to Table 1.

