#### **8.2 Dose escalation scheme for phase I**

Cohorts of 3-6 patients each will be treated with increasing doses of ruxolitinib in a progression of 10mg, 15mg, 25 mg and 50 mg twice daily.

At least 3 patients will be treated at each dose level. All patients treated at the preceding dose level will be observed a minimum of 5 weeks before dose escalation occurs. Dose escalation will proceed as follows:

- If none of the initial 3 evaluable patients in a cohort experiences first cycle dose limiting toxicity (DLT), then a new cohort of 3 patients will be treated at the next higher dose level.
- If one of 3 evaluable patients in a cohort experiences DLT, then up to an additional 3 patients will be treated at the same dose level. Escalation will continue if only one of the 6 patients experiences a DLT.
- In the event that 2 of 3 evaluable patients, or 2 of 6 patients in the first cohort experiences a DLT, then the next cohort of patients will be treated at a lower dose level (dose level -1) and no further dose escalation will occur in this step. Three patients will be enrolled at this dose level, if 0 or 1 patients experiences a DLT, a further 3 patients will be enrolled at this dose level. If overall 0 or 1 patient experiences a DLT at this dose level, this dose will be established as the maximum tolerated dose (MTD).
- If two or more evaluable patients in the cohort experience DLT, then the maximum tolerated dose (MTD) will have been exceeded, and no further dose escalation will occur. The previous dose will be considered as the MTD.
- If only three patients were treated at the dose level under consideration as the MTD, then up to an additional 3 patients will be accrued. If no more than one patient at that dose level experiences DLT, then that dose level will be confirmed as the MTD. If two or more patients in that cohort experience DLT, then the previous dose level will be studied in the same fashion.

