### **8.3 Definition of DLT and MTD:**

For the purposes of assessing safety, DLTs will be defined as those adverse events occurring in the first cycle (i.e. 28 days) of therapy that are not clearly related to disease, intercurrent illness or concurrent medication. These events will be defined based on the NCI CTCAE version 4 as follows:

- Any Grade 3 or higher non-hematologic toxicity (with the exceptions of Grade 3 or higher nausea, vomiting, or diarrhea, which will be considered DLTs only after optimal prophylactic measures have been prescribed; Grade 3 elevations of AST/ALT must be sustained for more than 4 days or reach Grade 4 to be considered a DLT. Grade 3 elevations in bilirubin must occur in the setting of a direct bilirubin  $>1$  to be considered a DLT. Fatigue must be Grade 4 to be considered a DLT)
- Any Grade 4 hematologic toxicity lasting at least 42 days from the first day of the last cycle of therapy with a bone marrow cellularity of  $\leq 5\%$  and no evidence of leukemia. No dose modification will occur until any potential DLTs is fully assessed

MTD is defined as the highest dose studied for which the incidence of DLT is less than 17% (1 out of 6).

**Table 2 - Criteria for dose modifications of RUXOLITINIB due to study drug-related toxicity – These must be clearly related to ruxolitinib and not the underlying disease; to be determined by PI and treating physician**

Worst Toxicity CTCAE Grade* unless otherwise specified (Value)	Dose Modification Guidelines At any time during a cycle of therapy (including intended day of dosing)	
HEMATOLOGICAL TOXICITIES		
Thrombocytopenia	< 20 x 10  /L	Interrupt study treatment dosing until resolved to ≥ 20 x 10  /L, then restart study treatment at reduced level as per Table 5
	> 20 x 10  /L + grade 3 bleed	Interrupt study treatment dosing until bleeding is resolved and platelet count is at level before bleed was noted, then resume study treatment at reduced level as per Table 5
Neutropenia (ANC)	Grade 4 (ANC < 0.5 x 10  /L)	Interrupt study treatment dosing until resolved to ≤ grade 2, or baseline, then: 
 
• If resolved within 7 days restart study treatment at an unchanged dose level
 
• If resolved in more than 7 days then restart study treatment at reduced level as per Table 5
 

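### Two unranked rules govern ruxolitinib restart after drug-related cytopenia in induction, and only one asks for count recovery; separately, no dose is defined below 10 mg BID

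*Combined protocol and SAP*

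**What the plan says.** **Restart after cytopenia, Section 8.1.** The dose-modification text for induction in both phases deals with significant myelosuppression thought to be due to ruxolitinib: "it can be held for a week and then resumed at a lower dose (5-10 mg per day less than the prior dose". It gives no platelet or neutrophil level, either as the trigger or as a condition for restart. The same text adds two further routes: "Adjustment of dose of RUXOLITINIB to 15 mg BID or 10 mg BID are acceptable in patients who have toxicity" (for those who are benefiting), and "Other dose modification schedules felt to be in the best interest of the patient may be permitted" after a documented discussion with the principal investigator.

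**Restart after cytopenia, Table 2 (Section 8.3).** The table is limited to ruxolitinib toxicity ("These must be clearly related to ruxolitinib and not the underlying disease"), and its column header applies it throughout a cycle, so induction is included. It advises interruption until platelets are back to at least 20 x 10^9/L. For grade 4 neutropenia the condition is ANC at grade 2 or better, or baseline. For febrile neutropenia it is resolved fever and ANC at grade 2 or better. Restart is at a reduced level taken from Table 5, except that grade 4 neutropenia resolving within 7 days leads to an unchanged dose.

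**Reductions by level.** Section 8.2 says that if the first cohort has 2 DLTs the next cohort "will be treated at a lower dose level (dose level -1". The phase I summary in Section 8.1 has "3 patients will be treated at the next lower dose level according to Table 1". A patient with extramedullary toxicity "may receive a second induction course at the next lower dose with respect to RUXOLITINIB". Tables 1 and 5 both begin at level 0, 10 mg BID.

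**The concern.** Both restart rules need attribution to ruxolitinib, and both are live in induction. No sentence ranks them. A physician who reads Section 8.1 alone could therefore re-dose a myelosuppressive drug after seven days in a patient still at platelets below 20 x 10^9/L or ANC below 0.5 x 10^9/L, where Table 2 would keep the drug on hold. The two rules also give different restart doses, so patients with the same event could be handled differently with no deviation recorded.

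The missing level is a separate matter. If the starting cohort proves too toxic, the protocol orders a de-escalation to a dose that it never states.

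**Working it through.** The plan gives no figure to reproduce here. The check is a comparison of texts, plus arithmetic on the dose ladder.

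**Step 1. The rules side by side (induction, event attributed to ruxolitinib)**

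| Event | Section 8.1 one-week option | Table 2 |
|---|---|---|
| Platelets <20 x 10^9/L | Restart after 7 days, 5-10 mg/day less, no count condition | Hold until ≥20, then reduced level |
| Grade 4 neutropenia, resolves in >7 days | Same | Hold until grade 2 or better, or baseline, then reduced level |
| Grade 4 neutropenia, resolves within 7 days | Same (dose lowered) | Unchanged dose |
| Febrile neutropenia | Same | Hold until afebrile and ANC grade 2 or better, then reduced level |
| Anemia | Same, if counted as myelosuppression | Reductions only after cycle 6, so no clash over reductions in induction |

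In the first, second and fourth rows, Section 8.1 read literally allows restart before recovery whenever recovery takes more than 7 days. In the third row it is the more cautious rule on dose.

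**Step 2. Restart dose.** Inputs are the Table 5 doses. Daily total = 2 x BID dose. Section 8.1 dose = daily total minus 5 to 10 mg. Table 2 dose = next lower row (assumed, because the table does not say how many rows).

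| Current dose | Daily total | Section 8.1 option | One row down |
|---|---|---|---|
| 50 mg BID | 100 mg | 90-95 mg | 50 mg |
| 25 mg BID | 50 mg | 40-45 mg | 30 mg |
| 15 mg BID | 30 mg | 20-25 mg | 20 mg |
| 10 mg BID | 20 mg | 10-15 mg | none |

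At 25 mg BID, the phase II target, the ratio of the Section 8.1 dose to the Table 2 dose is 40/30 = 1.33 to 45/30 = 1.50. If a benefiting patient is instead moved to 15 or 10 mg BID, as Section 8.1 also accepts, the ratio is 30/30 = 1.00 or 20/30 = 0.67. After grade 4 neutropenia that resolves within 7 days, Table 2 keeps 50 mg/day, so the ratio is 40/50 = 0.80 to 45/50 = 0.90.

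**Step 3. Do existing checks close the gap?** The protocol states that "Patients with prolonged cytopenias should have a bone marrow exam around day 42". A hold that starts before day 42 - 7 = 35 reaches its one-week restart before that examination, whose purpose is to separate drug effect from persistent disease. Table 3 has a CBC at least weekly in cycle 1, so a count should be at hand, but Section 8.1 does not make restart depend on it. From cycle 2 the minimum is every 2 weeks, so in a second induction course no CBC need fall at a one-week restart.

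**Step 4. Below 10 mg BID.** Section 13 starts phase I at level 0 and calls a level with 2 DLTs the stopping dose. It defines the MTD as the highest level with 6 treated and at most 1 DLT. Failure at level 0 would then leave no MTD. Section 8.2 instead orders a further cohort at level -1, which has no dose in either table. Table 2's reduced restart and the two next-lower-dose instructions in Section 8.1 fail at 10 mg BID for the same reason.

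**The case against.** The strongest reply is that the two rules can be read together. Section 8.1 is permissive, and its trigger is undefined. It could be meant for milder cytopenia (for example platelets of 20-50 x 10^9/L), with the more specific Table 2 taking over at its own thresholds. Table 2 is itself headed as guidelines, and the principal investigator may agree other schedules. All of this is fair. A reader might infer that the protocol directs re-dosing before recovery, or that a physician who follows Table 2 breaches Section 8.1. The documents support neither. What stands is that the sensible reading is nowhere written down, and the literal one is open.

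A reader might also infer that Section 8.1 always gives the higher dose. It does not, as the neutropenia row and the 15 and 10 mg BID alternatives show.

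On monitoring, the CBC frequencies are minimums, and good practice would add a count before restart. That is true, but it is not a stated condition.

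On the missing level, Section 13 implies that failure at 10 mg BID ends with no MTD, and an individual patient at 10 mg BID can still drop to 10-15 mg/day under Section 8.1. So it would be wrong to say that no reduction is possible there. Neither point gives level -1 a dose.

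**Conclusion.** The concern holds as a gap in precedence and a gap in the dose table. Once a Table 2 threshold is crossed, Section 8.1 can be read as allowing restart before recovery, and nothing in the protocol excludes that reading. At 25 mg BID the one-week option gives 1.33 to 1.50 times the Table 2 dose, on the assumption that a reduced level is one row down. The direction is mixed across events and across the Section 8.1 alternatives.

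The number of patients affected cannot be derived: both rules turn on attribution to ruxolitinib, and decitabine and the leukemia also lower counts. Nor can excess exposure be totalled, because the documents give no recovery times.

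The absence of a level -1 dose needs no interpretation. The step that Section 8.2 orders after a failed first cohort cannot be carried out as written. Sample size and stopping boundaries are not affected.

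A minor clarification belongs with this. Table 2 applies within cycle 1, whereas Sections 3.1 and 9.0 place dose modification after cycle 1, and Section 8.3 defers it until potential DLTs are assessed. It should be stated whether a reduced restart is allowed within cycle 1.

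**What to change.** 1. State that Table 2 governs whenever its thresholds are met, and that the Section 8.1 one-week option applies only to cytopenia above those thresholds. Require a CBC before restart that shows Table 2 recovery. Add a return-to-baseline alternative to the platelet row: the neutropenia row has one, and eligibility sets no platelet minimum, so without it some holds could run on indefinitely.
2. Define a reduced level as the next lower row of Table 5.
3. Add a level -1 row to Tables 1 and 5, for example 5 mg BID. This is 10 mg/day, already the lower end of the Section 8.1 option from 10 mg BID, and is feasible with the 5 mg tablets. Alternatively, state that a patient who needs a reduction at 10 mg BID discontinues ruxolitinib, and that phase I stops without an MTD if the first cohort fails.
4. Add one sentence on whether Table 2 holds and reduced restarts apply within cycle 1.

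The cost is a few sentences and one table row, at most one extra CBC per hold from cycle 2, and some longer holds. The last is a real cost, because Section 8.3 notes rebound symptoms when ruxolitinib is stopped, although it already allows a prednisone taper for them.
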